## 10. STUDY CALENDAR

Pre-study screening evaluations are to be conducted within 42 days prior to registration. All cycles are 28 days in duration. There are no rest periods between cycles. Whenever possible, the study visit should occur on the scheduled visit day. A ± 5-day window is allowed in order to accommodate participants' schedules.

	Screening	Pre-Treatment 	Cycle 1			Pre-Cycles 2, 3	Pre-Cycles 4, 5, 7, 8, 10, 11	Pre-Cycles 6, 9, 12	Relapse	End of Treatment 	Follow-Up 
	Pre-HSCT	D-14	D1 	D8	D15						
Informed Consent	X										
Medical History	X	X									
Physical Exam	X	X	X	X	X	X	X	X	X	X	
Vitals (BP, HR, RR)	X	X	X	X	X	X	X	X	X	X	
Performance Status	X	X	X							X	
12-lead ECG	X		X	X	X	X	X	X	X	X	
Echocardiogram or MUGA scan	X										
CBC w/ diff	X	X	X	X	X	X	X	X	X	X	
Chemistries 	X	X	X	X	X	X	X	X	X	X	
GVHD assessment 		X	X	X	X	X	X	X		X	X
Peripheral blood chimerism			X					X	X	X	
Coagulation parameters (PT, PTT, INR, D-dimer, fibrinogen)	X	X	X	X	X	X	X	X	X	X	
Pregnancy Test 	X		X			X	X	X		X	
Bone Marrow Biopsy and Aspirate 	X	X						C6 and C12 only	X		
Adverse Event Evaluation	X		X	X	X	X	X	X	X	X	X
Blood for correlative studies (2-HG, NGS)		X		X	X	X			X		

CONFIDENTIAL

This document is confidential. Do not disclose or use except as authorized.

WGS)											
Survival											X
Disease Assessment 							C6 and C12 only	X			
New Antineoplastic Therapy 											X

 Pre-treatment evaluations are to be conducted within 14 days prior to start of protocol therapy. Pre-treatment bone marrow biopsy is to be conducted after neutrophil engraftment (defined as ANC  $\geq 1000/\mu\text{L}$ ). In the event that the participant's condition is deteriorating, laboratory evaluations should be repeated within 48 hours prior to initiation of the next cycle of therapy.

 Any evaluations that are required at both pre-treatment and Cycle 1 Day 1 do not need to be repeated on Cycle 1 Day 1 if they were done in the previous 7 days.

 Cycle 1 Day 1 assessments must be performed prior to administration of ivosidenib. Patients must fulfill Day 1 laboratory criteria as outlined in Section 5.2.1.

 Chemistries include sodium, potassium, calcium, magnesium, phosphorus, chloride, blood urea nitrogen (BUN), total bilirubin, direct bilirubin, creatinine, albumin, total protein, alkaline phosphatase, alanine aminotransferase (ALT), aspartate aminotransferase (AST), lactate dehydrogenase (LDH).

 Symptoms of both acute and chronic GVHD should be assessed. Criteria are listed in section 11.2 and 11.3.

 Pregnancy test is only required for women of childbearing potential. This must be done within 7 days prior to study drug administration at each cycle.

 An End of Treatment visit should occur within 5 days of the last dose of study drug. If the required evaluations have been performed as part of another study visit, they do not need to be repeated.

 Disease assessment will be based on modified IWG criteria or other appropriate response criteria for the malignancy being studied.

 Follow-up data will be collected every 3 months for 24 months from the start of treatment until participant withdrawal, change of therapy following conclusion of study treatment, removal from study, or death. These evaluations may occur at an outside hospital or clinic, as long as documentation is received by the study site for reporting purposes.

 All new therapies administered after the last dose of ivosidenib are to be captured during follow-up.

 Post-transplant bone marrow biopsies and aspirates are allowed a  $\pm 1$  month window

## 11. MEASUREMENT OF EFFECT

Although response is not the primary endpoint of this trial, participants will be assessed by standard criteria for disease assessment. Response will be assessed through the evaluation of bone marrow biopsies and/or aspirates along with complete blood counts and differentials. Treatment decisions will be based on the treating physician's assessment.

Disease will be assessed while on study drug treatment prior to cycles 6 and 12, and/or at any time that progression of disease is suspected. An assessment will also be done at the End of Treatment study visit for participants who discontinue ivosidenib for a reason other than disease progression.

### 11.1 Assessment / Response Criteria

#### 11.1.1 AML

##### Recurrence/Morphologic Relapse:

- Reappearance of leukemic blasts in the peripheral blood or

CONFIDENTIAL

This document is confidential. Do not disclose or use except as authorized.

- $\geq 5\%$  blasts in the bone marrow not attributable to any other cause Development of extramedullary disease
- The appearance of new dysplastic changes should be considered relapse.
- The reappearance or development of cytologically proven extramedullary disease indicates relapse.
- Molecular and/or genetic relapse is characterized by reappearance of a cytogenetic or molecular abnormality.

**Complete remission (CR):**

- Bone marrow showing less than 5% myeloblasts with normal maturation of all cell lines,
- ANC of at least 1000/ $\mu$ L
- Platelet count of 100,000/ $\mu$ L
- Absence of blasts in peripheral blood
- Absence of identifiable leukemic cells in the bone marrow
- Absence of extramedullary disease.

If possible, at least one bone marrow biopsy should be performed to confirm CR.

**Complete Remission with Incomplete Blood Count Recovery (CRi):**

- Same as for CR but without achievement of ANC at least 1000/uL (CRi) and/or platelet count of 100,000/uL (CRp).

**Partial Remission:**

- All hematologic criteria of CR are fulfilled, and
- A decrease of bone marrow blast percentage to 5% to 25%, and
- Decrease of pretreatment bone marrow blast percentage by at least 50%.

**Morphologic Leukemia Free State:**

- Bone marrow blasts <5%;
- Absence of blasts with Auer rods;
- Absence of extramedullary disease;
- No hematologic recovery required

**Resistant Disease:**

- Failure to achieve CR or CRi.

### 11.1.2 MDS and CMML (Savona 2015)

**Disease Progression**

Combination of 2 major criteria, 1 major and 2 minor criteria, or 3 minor criteria from list

**Major Criteria**

- Increase in blast count
  - Less than 5% blasts:  $\geq 50\%$  increase and to  $> 5\%$  blasts
  - 5% - 10% blasts:  $\geq 50\%$  increase and to  $> 10\%$  blasts

---

CONFIDENTIAL

This document is confidential. Do not disclose or use except as authorized.

- 10% - 20% blasts:  $\geq 50\%$  increase and to  $> 20\%$  blasts
- 20% - 30% blasts:  $\geq 50\%$  increase and to  $> 30\%$  blasts
- Evidence of cytogenetic evolution
  - Appearance of a previously present or new cytogenetic abnormality in complete cytogenetic remission via FISH or classic karyotyping
  - Increase in cytogenetic burden of disease by  $\geq 50\%$  in partial cytogenetic remission via FISH or classic karyotyping
- New extramedullary disease
  - Worsening splenomegaly
  - Progressive splenomegaly that is defined by IWG-MRT: the appearance of a previously absent splenomegaly that is palpable at  $> 5$  cm below the left costal margin or a minimum 100% increase in palpable distance for baseline splenomegaly of 5-10 cm or a minimum 50% increase in palpable distance for baseline splenomegaly of  $> 10$  cm
  - Extramedullary disease outside of the spleen
    - To include new/worsening hepatomegaly, granulocytic sarcoma, skin lesions, etc.

### ***Minor Criteria***

- Transfusion dependence
- Significant loss of maximal response on cytopenias  $\geq 50\%$  decrement from maximum remission/response in granulocytes or platelets
- Reduction in hemoglobin by  $\geq 1.5$  g/dL from best response or from baseline as noted on complete blood count
- Increasing symptoms as noted by increase in  $\geq 50\%$  as per the MPN-SAF TSS
- Evidence of clonal evolution (molecular)

### **Complete Remission:**

Presence of all of the following improvements:

- Bone marrow  $\leq 5\%$  myeloblasts (including monocytic blast equivalents in case of CMML) with normal maturation of all cell lines and return to normal cellularity
- Osteomyelofibrosis absent or equal to “mild reticulin fibrosis” ( $\leq$  grade 1 fibrosis)
- Peripheral blood:
  - Hemoglobin  $\geq 11$  g/dL
  - Platelets  $\geq 100,000/\mu\text{L}$ ;  $\leq 450,000/\mu\text{L}$
  - Neutrophils  $\geq 1000/\mu\text{L}$
  - WBC  $\leq 10,000$  cells/  $\mu\text{L}$
  - Blasts 0%
  - Neutrophil precursors reduced to  $\leq 2\%$
  - Monocytes  $\leq 1000/\mu\text{L}$
- Complete resolution of extramedullary disease present before therapy (e.g. cutaneous disease, disease-related serous effusions), including palpable hepatosplenomegaly
- Persistent low-level dysplasia is permitted given subjectivity of assignment of dysplasia

### **Partial Remission:**

- Normalization of peripheral counts and hepatosplenomegaly with bone marrow blasts

---

CONFIDENTIAL

This document is confidential. Do not disclose or use except as authorized.

(and blast equivalents) reduced by 50%, but remaining  $> 5\%$  of cellularity *except* in cases of MDS/MPN with  $\leq 5\%$  bone marrow blasts at baseline

### **Marrow Response**

- Optimal marrow response: Presence of all marrow criteria necessary for CR without normalization of peripheral blood indices as presented above.
- Partial marrow response: Bone marrow blasts (and blast equivalents) reduced by 50%, but remaining  $> 5\%$  of cellularity, *or* reduction in grading of reticulin fibrosis from baseline on at least 2 bone marrow evaluations spaced at least 2 months apart

### **Complete Cytogenetic Response**

- Resolution of previously present chromosomal abnormality (known to be associated with myelodysplastic syndrome, myeloproliferative neoplasms, or MDS/MPN), as seen on classic karyotyping with minimal of 20 metaphases or FISH

### **Clinical Benefit**

Requires 1 of the following in the absence of progression or CR/partial response and independent of marrow response to be considered a clinical benefit:

- Erythroid response
  - Hgb increase by  $\geq 2.0$  g/dL
  - Transfusion Independence (TI) for  $\geq 8$  weeks for patients requiring at least 4 packed red blood cell transfusions in the previous 8 weeks
  - Only red blood cell transfusions given based on physician's judgment for a pretreatment Hgb of  $\leq 8.5$  g/dL will count in the red blood cell TI response evaluation.
- Platelet response
  - Transfusion independence when previously requiring platelet transfusions of at least a rate of 4 platelet transfusions in the previous 8 weeks
  - Pretreatment  $\leq 20 \times 10^9/L$ : increase from  $< 20 \times 10^9/L$  to  $> 20 \times 10^9/L$  and by at least 100%
  - Pretreatment  $> 20 \times 10^9/L$  but  $\leq 100 \times 10^9/L$ : absolute increase of  $\geq 30 \times 10^9/L$
- Neutrophil response
  - Pretreatment  $\leq 0.5 \times 10^9/L$ : at least 100% increase and an absolute increase  $\geq 0.5 \times 10^9/L$
  - Pretreatment,  $> 0.5 \times 10^9/L$  and  $\leq 1.0 \times 10^9/L$ : at least 50% increase and an absolute increase  $\geq 0.5 \times 10^9/L$
- Spleen response
  - Either a minimum 50% reduction in palpable splenomegaly of a spleen that is at least 10 cm at baseline or a spleen that is palpable at more than 5 cm at baseline becomes not palpable
- Symptom response
  - Improvement in symptoms as noted by decrease of  $\geq 50\%$  as per the MPN-SAF TSS scoring  $< 20$  were not considered eligible for measuring clinical benefit.

---

CONFIDENTIAL

This document is confidential. Do not disclose or use except as authorized.

## 11.2 Acute GVHD

Participants will be evaluated for the presence or absence of acute GVHD at various timepoints as defined in Section 10. Clinical stage and grade of acute graft-versus-host-disease (GVHD) is based on Przepiorka et al, 1995.

### Clinical Stage

Stage	Skin	Liver	Intestinal Tract
			Bilirubin: SI units
1	Maculopapular rash < 25% of body surface area	34-50 µmol/L (2-3 mg/dL)	> 500 mL diarrhea / day
2	Maculopapular rash 25% - 50% of body surface area	51-102 µmol/L (3.1 – 6 mg/dL)	> 1000 mL diarrhea / day
3	Rash > 50% of body surface	103 – 225 µmol/L (6.1 – 15 mg/dL)	> 1500 mL diarrhea / day
4	Generalized erythroderma with bullous formation	> 225 µmol/L (> 15 mg/dL)	Severe abdominal pain, with or without ileus

(a) Use the “Rule of Nines” or burn chart to determine the extent of the rash.

### Grade

Grade	Skin	Liver	Intestinal Tract
I	Stage 1-2	None	None
II	Stage 3 or	Stage 1 or	Stage 1
III	--	Stage 2-3 or	Stage 2-4
IV	Stage 4 or	Stage 4	--

## 11.3 Chronic GVHD

Participants will be evaluated for the presence or absence of chronic GVHD at various timepoints as defined in Section 10. Chronic GVHD will be assessed as per the National Institutes of Health consensus development project on criteria for clinical trials in chronic graft-versus-host disease – see Appendix D.

The diagnosis of chronic GVHD requires the following:

- Distinction from acute GVHD
- Presence of at least 1 diagnostic clinical sign of chronic GVHD or presence of at least 1 distinctive manifestation confirmed by pertinent biopsy or other relevant tests.
- Exclusion of other possible diagnoses.
- Scoring of organ manifestations requires careful assessment of signs, symptoms, laboratory values, and other study results. A clinical scoring system (0-3) is provided for evaluation of the involvement of individual organs and sites. The proposed global assessment of severity (mild, moderate, or severe) is derived by combining organ- and site-specific scores.

Overall Scoring (compiled from individual organ scores shown in the Appendix):

- Mild – involves only 1 or 2 organs or sites (except the lung), with no clinically significant

CONFIDENTIAL

This document is confidential. Do not disclose or use except as authorized.

- functional impairment (maximum score of 1 in all affected organs or sites).
- Moderate – involves (1) at least 1 organ or site with clinically significant but no major disability (maximum score of 2 in any affected organ or site) or (2) 3 or more organs or sites with no clinically significant functional impairment (maximum score of 1 in all affected organs or sites). A lung score of 1 will also be considered moderate cGVHD.
- Severe – indicates major disability caused by cGVHD (score of 3 in any affected organ or site). A lung score of 2 will also be considered severe cGVHD.

## 11.4 Endpoints

Overall Survival (OS): Overall Survival is defined as the time from first dose of study drug to the date of death due to any cause. Participants who are alive at the analysis / cutoff date will be censored at the last contact date.

Relapse-Free Survival (RFS): Relapse-Free Survival is defined as the time from first dose of study drug to the earlier of relapse or death due to any cause. Participants alive without disease progression are censored at the date of last disease evaluation.

*IDH* clonal evolution and mutational burden will be explored with descriptive and graphical methods. Identification of factors that influence the relationship of mutations with safety and efficacy endpoints will be explored, as appropriate. Summary statistics, including the mean, standard deviation, median, minimum, maximum, and 25th and 75th percentiles for 2-HG and allele burdens will be recorded at each time point. Although exploratory and insufficiently powered to detect survival differences, we will attempt to assess the relationships of relapse-free survival and overall survival with 2-HG levels and/or *IDH* mutational burden.

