## **5.7 Duration of Follow Up**

Participants will be followed for 24 months from the start of protocol therapy or until death, whichever occurs first. Participants removed from protocol therapy for unacceptable adverse event(s) will be followed until resolution or stabilization of the adverse event. Participants who

---

CONFIDENTIAL

This document is confidential. Do not disclose or use except as authorized.

conclude or are removed from protocol treatment and begin a new therapy will be followed for survival only. Adverse event and toxicity data will not be collected for patients who initiate new therapy. Follow-up assessments for study purposes will occur every 3 months per the study calendar in Section 10.

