#### **6.3.1 250 mg dosing**

If the participant was at the 250mg daily dosing level when the toxicity occurred, and it takes longer than 14 days for the event to resolve to  $\leq$  grade 1, then the participant will be taken off treatment and will remain on study only for survival and other outcomes.

If the toxicity takes less than 14 days to resolve to  $\leq$  grade 1, then ivosidenib can be restarted at 250mg daily dosing upon resolution. If the attributable toxicity recurs at  $\geq$  grade 3 (or grade 4 bilirubinemia in those with known Gilbert’s disease – see above section 6.3) during the course of the study, then the participant will come off treatment and will remain on study only for survival and other outcomes. If the toxicity recurrence (to  $\geq$  grade 3) happens during the first cycle of dosing, then the event will be a DLT.

---

CONFIDENTIAL

This document is confidential. Do not disclose or use except as authorized.

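### RFS counts deaths to month 24 but censors event-free participants at their last disease evaluation, scheduled no later than about month 11, so the later Kaplan-Meier curve is biased downward

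*Combined protocol and SAP*

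**What the plan says.** Section 11.4 defines RFS from first dose to the earlier of relapse or death from any cause, with no upper limit on when a death counts. The censoring rule is: "Participants alive without disease progression are censored at the date of last disease evaluation". OS, defined just above it, is censored at last contact.

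Section 11 places disease assessments on treatment "prior to cycles 6 and 12, and/or at any time that progression of disease is suspected". It adds: "An assessment will also be done at the End of Treatment study visit for participants who discontinue ivosidenib", limited to stops for reasons other than progression. Footnote 7 of the Study Calendar (section 10) fixes that visit: "An End of Treatment visit should occur within 5 days of the last dose of study drug". On cycle length the calendar says: "All cycles are 28 days in duration. There are no rest periods between cycles". Section 5.2.2 sets 12 cycles. The calendar's Follow-Up column lists GVHD, adverse events, survival and new therapy, but no marrow, blood count or disease assessment.

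Section 5.7 says: "Participants will be followed for 24 months from the start of protocol therapy or until death, whichever occurs first". Those who "conclude or are removed from protocol treatment and begin a new therapy will be followed for survival only". Under section 6.3.1, a participant whose toxicity is slow to resolve "will be taken off treatment and will remain on study only for survival and other outcomes". Section 13 plans Kaplan-Meier estimates of RFS, and section 11.4 plans to relate RFS to 2-HG and *IDH* mutational burden.

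**The concern.** The two parts of the RFS definition run on different clocks. A participant who dies at month 18 stays in the risk set until month 18. A participant who is well at month 24 leaves it at about month 11, because no evaluation is scheduled after that. Who is censored early is thus decided by what happens later, which breaks the independent-censoring condition that Kaplan-Meier needs. The few late events are divided by a risk set from which the event-free have largely been removed.

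The reported curve could fall steeply, even to zero, while most participants are alive and in remission. The OS curve would follow the same event-free people to about month 24, so the two curves could not be read together. The planned biomarker comparisons would use the same distorted times.

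**Working it through.** The plan states no RFS figure, so there is none to reproduce.

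**Timing** (sections 5.2.2, 5.7, 10 and 11)
- Pre-cycle 12: 11 × 28 + 1 = day 309.
- End of cycle 12: 12 × 28 = day 336.
- Latest End of Treatment visit: 336 + 5 = day 341.
- Follow-up: 24 months, about day 730.
- Time with no scheduled evaluation: 730 − 341 = 389 days (53%) to 730 − 309 = 421 days (58%).

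**Exact example.** Use n = 16, the number section 13 plans at the RP2D. Assume 4 events by day 336 and 12 participants event-free, so S = 12/16 = 0.75. Then k of the 12 die later, and m of the remaining 12 − k have a negative evaluation dated on or after the last of those deaths.
- As written: S = 0.75 × m/(m + k).
- Consistent censoring: S = 0.75 × (12 − k)/12.

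| m | k = 1 | k = 3 |
|---|---|---|
| 0 | 0% | 0% |
| 1 | 37.5% | 18.75% |
| 3 | 56.25% | 37.5% |
| 6 | 64.3% | 50% |
| Consistent censoring | 68.75% | 56.25% |

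The two rules agree only when every other event-free participant has a later evaluation (m = 11 for k = 1, m = 9 for k = 3).

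**Before month 11.** Suppose 4 of 16 stop event-free at about day 84 and one of them dies at day 200. As written, the other three are censored at day 84, so S = 12/13 = 92.3%. Consistent censoring gives 15/16 = 93.75%. The early bias exists but is small.

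**Illustration under assumed rates.** The setup was 3,000 simulated trials of 16 with exponential event times and the last scheduled evaluation at day 336. A share f of event-free participants has one later negative evaluation, uniform to day 730. Later events that are not captured are censored at the scheduled evaluation. Where no later event is captured, the last Kaplan-Meier value is carried forward to day 730. With an assumed true 24-month RFS of 60%:

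| f | Mean KM at day 730, 30% of later events captured | Mean KM at day 730, all captured |
|---|---|---|
| 0 | 29.7% | 2.8% |
| 0.10 | 38.3% | 8.7% |
| 0.25 | 46.8% | 16.3% |
| 0.50 | 53.6% | 25.1% |

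At f = 0.25, the curve ends at zero in 42% and 55% respectively of trials with a later event. With true RFS of 50, 60, 70 and 80% at f = 0.25, the mean is 36.1, 46.8, 56.7 and 68.9% (30% captured) and 10.1, 16.3, 24.8 and 39.3% (all captured). Every cell lies below the assumed truth.

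**The case against.** **Other evaluations may exist.** Section 11 allows assessment whenever progression is suspected, and it is unclear whether that continues after treatment. Those that confirm relapse add late events; only negative ones help, and participants who are well have no scheduled reason to have one. Section 9.3 also asks for an MRD sample at discontinuation from study. But section 5.8 takes participants off study only for loss to follow-up, withdrawal of consent or death, so someone well at month 24 gets no evaluation by that route.

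**The dates are not exact.** Footnote 11 allows marrows a window of one month either side, and long dose holds can shift cycles. The last evaluation could fall near month 12 (336 + 30 = day 366). That is fair, but repeating the simulation with day 366 changed little.

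**Some late deaths may go uncollected.** Footnote 9 ends follow-up at a change of therapy, whereas section 5.7 continues it for survival. The two need reconciling, but this touches only participants who start new therapy.

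**The size rests on assumptions, and the endpoint is minor.** This stands. The fall to 0% needs no later negative evaluation in anyone. At k = 1 and m = 6 the gap is 68.75 − 64.3 = about 4.4 points, against a binomial standard error for 11/16 of √(0.6875 × 0.3125/16) = 11.6 points. The simulated means include trials in which the curve really ended at about month 11. RFS is an exploratory objective in section 1.4, although section 13 lists it with the secondary endpoints.

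**The remedy is imperfect.** Also true in part: section 11.1.1 defines AML relapse partly by marrow and molecular findings, so a contact without marrow can miss or date late some relapses. That is a small upward error, not a reason to keep the present rule.

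**Conclusion.** The concern holds. As written, the rule biases Kaplan-Meier RFS downward after about month 11 (month 12 at the latest with the marrow window) whenever a later event is recorded, unless nearly all event-free participants happen to have later evaluations. Under the scheduled assessments alone, the last such event takes the curve to zero. With no later event the curve merely ends, which is limited follow-up and not bias.

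The mechanism and direction follow from the documents. The size depends on the event rate, the share of later events captured and the share of event-free participants with later evaluations, none of which the documents give. The RP2D decision is unaffected, as are the first 10 to 11 months for participants who complete 12 cycles. This should be corrected, but it does not threaten the primary objective.

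**What to change.** Preferred: in section 11.4, censor RFS at the last date on which the participant is known to be alive and relapse-free, whether from a disease evaluation or a follow-up contact. Record relapse status and date at the existing 3-monthly contacts, including for participants who start a new therapy. Align section 5.7 and footnote 9 of the calendar with this. State that relapse after treatment is ascertained without scheduled marrow, so some relapses may be found late.

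Alternative: report RFS only to one common cut-off, about 11 months from first dose. Count all events before it, censor event-free participants there, and say how relapse status is known up to the cut-off for those who stop early. This gives up any estimate beyond that point.

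In either case, print numbers at risk under the curve.

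Cost: one censoring sentence, matching wording in the follow-up text, and a relapse status and date field at contacts that already take place. The case report forms are not in the documents; if they already hold that field, only the text changes. No new visit or marrow is needed.
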